
Statistics
	
Three cohorts of patients will be prospectively included in the study:
 
1) Letrozole-stimulated cohort: this includes all newly diagnosed breast cancer who are candidates to receive (neo)adjuvant chemotherapy and undergo oocyte/embryo cryopreservation at the Belgian participating centres.
 
2) Standard-stimulated cohort: this includes all newly diagnosed breast cancer who are candidates to receive (neo)adjuvant chemotherapy and undergo oocyte/embryo cryopreservation at the French participating centres.
 
3) Non-stimulated cohort: this includes all newly diagnosed breast cancer who are candidates to receive (neo)adjuvant chemotherapy who have access

to the Fertility Clinics in all the participating centres but are not willing to undergo oocyte/embryo cryopreservation.

All the efficacy analyses will be performed to compare the letrozole-stimulated cohort and the standard-stimulated cohort. All the safety analyses will be conducted to compare separately the letrozole-stimulated cohort with the non-stimulated cohort and the standard-stimulated cohort with the non-stimulated cohort.

The sample size has been estimated based on the study primary endpoint (i.e. number of mature oocytes collected). With 113 patients in the standard-stimulated cohort and 113 in the letrozole-stimulated cohort, assuming a mean difference of 1.5 in the number of mature oocytes collected between the standard-stimulated cohort and the letrozole-stimulated cohort, the study will have a power of 0.80 to reject the null hypothesis of equal means with a standard deviation of 4.0 and with a significance level (alpha) of 0.05 using a two-sided two-sample equal-variance t-test. Considering that approximately one out of three (1:3) eligible patients counseled to undergo controlled ovarian stimulation for oocyte cryopreservation before starting anticancer treatments will accept the procedure, it is estimated to enroll 339 patients in the non-stimulated cohort.

Patients demographic, clinical and pathologic baseline characteristics will be compared in the three cohorts using chi-square test or Fisher Exact test for categorical variables and Wilcoxon rank-sum test or t-test for continuous variables, as appropriate. Dicothomous outcomes will be compared using

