involvement than women in the controlled ovarian stimulation group ( $p = 0.02$ ). After a mean follow-up of approximately 5 years, the study confirmed the absence of survival difference between the two groups, with an HR for recurrence after controlled ovarian stimulation of 0.77 (95% CI, 0.28-2.13;  $p = 0.61$ ). Although the numbers were limited, the authors performed several subgroup analyses showing that, apparently, neither *BRC A* mutation status ( $p = 0.57$ ), nor hormone-receptor status ( $p = 0.75$ ) nor undergoing controlled ovarian stimulation before or after breast surgery ( $p = 0.44$ ) seemed to affect survival in the controlled ovarian stimulation group [25]. Taking into account these results, all major international guidelines consider this strategy as standard in breast cancer patients [2,13–15]. However, during oncofertility counseling, it should be made clear that limited data are available to strongly support the safety of this procedure in breast cancer patients.

Of note, the first studies investigating the use of letrozole for assisted reproductive technology (ART) showed a potential increased risk of congenital cardiac and musculoskeletal anomalies in the newborns [26]; hence, its manufacturer issued a warning to physicians to stop using letrozole for this purpose in pre-menopausal women. However, subsequent studies did not confirm these findings [27–29]. Recently, a large Japanese study including 3,136 natural cycles and 792 letrozole-induced cycles investigated the risk of major congenital anomalies, pregnancy and neonatal outcomes with the use of letrozole in patients undergoing ART [30]. The study showed that the risk of miscarriage was significantly lower in women treated with letrozole (adjusted odds ratio [OR], 0.37; 95% CI, 0.30-0.47;  $p < 0.001$ ). Furthermore, the overall risk of major congenital anomalies was similar between the two groups (natural cycle 1.5% vs. letrozole 1.9%; adjusted OR, 1.24; 95% CI, 0.64-2.40;  $p = 0.52$ ), as well as the risk for any specific organ system malformation. Finally, no difference in all the other pregnancy and neonatal outcomes was observed between the two groups [30]. Hence, although these results support the safety of letrozole for assisted reproductive technology (ART), in some countries like France this compound cannot be used as part of controlled ovarian stimulation.

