## 5. STATISTICS

Three cohorts of patients will be prospectively included in the study (Figure 1 in the Appendix):

**1) Letrozole-stimulated cohort:** this includes all newly diagnosed breast cancer who are candidates to receive (neo)adjuvant chemotherapy and undergo oocyte/embryo cryopreservation at the Belgian participating centres.

**2) Standard-stimulated cohort:** this includes all newly diagnosed breast cancer who are candidates to receive (neo)adjuvant chemotherapy and undergo oocyte/embryo cryopreservation at the French participating centres.

**3) Non-stimulated cohort:** this includes all newly diagnosed breast cancer who are candidates to receive (neo)adjuvant chemotherapy who have access to the Fertility Clinics in all the participating centres but are not willing to undergo oocyte/embryo cryopreservation. Patient who underwent another fertility preservation procedure (ovarian tissue cryopreservation, GnRH analogues,...) are eligible in this cohort.

All the efficacy analyses will be performed to compare the letrozole-stimulated cohort and the standard-stimulated cohort. All the safety analyses will be conducted to compare separately the letrozole-stimulated cohort with the non-stimulated cohort and the standard-stimulated cohort with the non-stimulated cohort.

To evaluate the efficacy of performing a controlled ovarian stimulation with or without letrozole in young women with newly diagnosed breast cancer who are candidates to receive (neo)adjuvant chemotherapy, the following endpoints will be assessed:

- Number of mature oocytes collected (primary endpoint).
- Number of oocytes collected;
- Maturation rate: defined as ratio between the number of mature oocyte collected and total number of oocyte collected;
- Number of oocyte/embryo cryopreserved;
- Number of patients with poor response: defined as retrieval of  $\leq 4$  oocytes;
- Number of patients with stimulation failure: defined as no follicular growth after 1 week of adequate controlled ovarian stimulation administration.

The efficacy of performing controlled ovarian stimulation with or without letrozole will be evaluated also in various subgroups of young women with newly diagnosed breast cancer who are candidates to receive (neo)adjuvant chemotherapy according to the following characteristics:

- Type of stimulation: follicular vs. random;
- Hormone receptor status: positive vs. negative;
- Presence of *BRCA* mutation: *BRCA*-mutated vs. *BRCA*-not mutated.

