The impact of anticancer therapies on patients' ovarian function will be evaluated in various subgroups of young breast cancer patients according to:

- Age: <30 vs. 30-35 vs. > 35;
- Type of chemotherapy received: anthracycline- and taxane-based vs. taxane-based vs. others;
- Number of months of chemotherapy received: <4 months vs. > 4 months;
- Exposure to platinum agents: use vs. no use.
- Exposure to endocrine therapy: use vs. no use.
- Exposure to anti-HER2 therapy: use vs. no use.
- Presence of *BRCA* mutation: *BRCA*-mutated vs. *BRCA*-not mutated.

The sample size has been estimated based on the study primary endpoint (i.e. number of mature oocytes collected). With 113 patients in the standard-stimulated cohort and 113 in the letrozole-stimulated cohort, assuming a mean number of mature oocytes collected of 6.1 in the standard-stimulated cohort, the study will have a power of 0.80 to reject the null hypothesis of equal means when the population mean difference is 1.5 mature oocytes collected (estimating a mean number of mature oocytes collected of 7.6 in the letrozole-stimulated cohort) with a standard deviation for both groups of 4.0 and with a significance level (alpha) of 0.05 using a two-sided two-sample equal-variance t-test. Considering that approximately one out of three (1:3) eligible patients counseled to

undergo controlled ovarian stimulation for oocyte cryopreservation before starting anticancer treatments will accept the procedure, it is estimated to enroll 339 patients in the non-stimulated cohort.

Patients demographic, clinical and pathologic baseline characteristics will be compared in the three cohorts using chi-square test or Fisher Exact test for categorical variables and Wilcoxon rank-sum test or t-test for continuous variables, as appropriate.

Dicothomous outcomes will be compared using univariate and multivariate logistic regression models. Time-to-event outcomes will be estimated and plotted using Kaplan-Meier methods. Survival rates will be compared using log-rank test and Cox proportional hazards models for univariate and multivariate analysis, respectively.

All tests will be two-sided and p-values of  $< 0.05$  will be considered statistically significant.

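### The primary comparison of mature oocytes is non-randomised and split by country, but Section 5 plans no adjusted analysis for it

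*Combined protocol and SAP*

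**What the plan says.** The design is a prospective cohort study without randomisation (Section 3). Section 5 defines the letrozole cohort as women who "undergo oocyte/embryo cryopreservation at the Belgian participating centres" and the standard cohort as those who "undergo oocyte/embryo cryopreservation at the French participating centres". Section 1 gives a reason for the split: "in some countries like France this compound cannot be used as part of controlled ovarian stimulation". The Synopsis, like Section 5, states: "All the efficacy analyses will be performed to compare the letrozole-stimulated cohort and the standard-stimulated cohort". The non-stimulated cohort is different. It takes women who "have access to the Fertility Clinics in all the participating centres but are not willing to undergo oocyte/embryo cryopreservation", so the complete overlap of cohort and country concerns the two stimulated cohorts only.

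The analysis text in Section 5, repeated in the Synopsis, names methods for three kinds of data:

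- baseline characteristics: chi-square, Fisher, Wilcoxon or t-test;
- dichotomous outcomes: univariate and multivariate logistic regression;
- time-to-event outcomes: Kaplan-Meier, log-rank and Cox models.

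No covariates are listed for any model. Nothing is named for a count or continuous outcome, and so nothing for the primary endpoint. A test is linked to that endpoint only in the sample-size calculation: "with a significance level (alpha) of 0.05 using a two-sided two-sample equal-variance t-test".

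**The concern.** In a non-randomised comparison, women at the Belgian and French centres may differ in age, ovarian reserve or other predictors of oocyte yield. An unadjusted comparison attributes any such difference to the stimulation programme. It can create an apparent effect or hide a real one. The planned baseline tests may reveal an imbalance but do not remove it from the estimate.

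The gap falls on the one analysis that answers the primary objective. Every method the plan names that could be applied to a count is unadjusted, while multivariate modelling is foreseen for other outcome types. Two secondary efficacy endpoints are dichotomous for each woman and so fall under the logistic models: "Number of patients with poor response: defined as retrieval of" at most four oocytes, and "Number of patients with stimulation failure: defined as no follicular growth after 1 week of adequate controlled ovarian stimulation administration".

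**Working it through.** **Inputs from Section 5.** 113 women per stimulated cohort; means 6.1 (standard) and 7.6 (letrozole); difference 1.5; SD 4.0 in both groups; two-sided alpha 0.05; power 0.80.

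**The plan's own figure.** SE = 4.0 × √(2/113) = 0.532. The noncentral t distribution gives power 0.801 at 113 per cohort and 0.798 at 112. The stated sample size therefore reproduces. The 95% half-width is 1.05 oocytes.

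**Bias of the unadjusted difference.** The documents give neither the correlation of a covariate with yield nor any Belgian-French imbalance; both are assumed here. Bias = correlation × 4.0 × imbalance in SD. Null rejection uses noncentrality bias/0.532. Power with the bias opposing the effect uses (1.5 − bias)/0.532.

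| Correlation | Imbalance (SD) | Bias (oocytes) | Null rejection | Power at 1.5, bias opposing |
|---|---|---|---|---|
| 0.2 | 0.1 | 0.08 | 5.3% | 0.76 |
| 0.3 | 0.1 | 0.12 | 5.6% | 0.73 |
| 0.3 | 0.2 | 0.24 | 7.3% | 0.65 |
| 0.4 | 0.2 | 0.32 | 9.2% | 0.60 |
| 0.5 | 0.3 | 0.60 | 20.2% | 0.39 |

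As a share of the planned difference, the bias runs from 0.08/1.5 = 5% to 0.60/1.5 = 40%.

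**Would the baseline tests catch it?** With 113 per cohort, a 5% test has power 0.12, 0.32 and 0.61 to detect imbalances of 0.1, 0.2 and 0.3 SD.

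**What adjustment gains.** Simulation with 30,000 runs per scenario, one prognostic and four noise covariates, robust (HC3) standard errors and no between-centre variation:

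| Scenario (correlation, SD) | Null rejection, t-test / adjusted | Power at 1.5 with opposing imbalance, t-test / adjusted | Adjusted half-width |
|---|---|---|---|
| 0.2, 0.1 | 5.4% / 4.7% | 0.76 / 0.80 | 1.06 |
| 0.4, 0.2 | 9.4% / 4.8% | 0.60 / 0.85 | 0.99 |
| 0.5, 0.3 | 20.0% / 4.4% | 0.39 / 0.88 | 0.94 |

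Five covariates plus cohort give 226/6 ≈ 38 women per slope, a modest model.

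**What adjustment does not gain.**

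- Measurement error: with covariate reliability 0.7 in the worst scenario, 0.60 × (1 − 0.7) = 0.18 oocytes of bias remain and null rejection is 6.4%.
- A residual country difference of 0.5 oocytes (assumed) is untouched: adjusted null rejection is 15% to 18%.
- Between-centre variation, in the 0.4, 0.2 SD scenario (number of centres and ICC assumed; the documents state neither):

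| Centres per country | ICC | Null rejection, t-test | Null rejection, adjusted |
|---|---|---|---|
| 6 | 0.01 | 11.7% | 7.4% |
| 6 | 0.05 | 19.0% | 16.1% |
| 3 | 0.01 | 13.9% | 9.5% |
| 3 | 0.05 | 27.7% | 26.5% |

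**The case against.** The strongest reply is that the complete overlap of cohort and country is a design limit that no covariate model repairs. That stands, and the figures above show it: a residual country difference passes through the adjusted model, and between-centre variation erodes much of the gain. The 4.4% to 4.8% rejection rate of the adjusted model holds only without either. What can be corrected is narrower: no analysis is named for the primary count, and no adjustment for measured case mix is planned.

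It is also fair that the harm rests on assumed inputs, is modest mid-range (7.3% against 5%), and arises only if the sample-size t-test becomes the analysis. The simulation uses a single linear predictor and does not address skew or zeros in the count. Eligibility (age 18 to 40, stage I to III, no prior gonadotoxic treatment, an ovarian-reserve criterion for stimulated women) may narrow case mix, although the reserve criterion is loose because its parts are joined by and/or. The baseline test detects the largest assumed imbalance more often than not; it misses mostly at 0.1 to 0.2 SD, where the harm is smaller. Detection still does not correct the estimate.

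One could argue that the Wilcoxon or t-test sentence covers the endpoint. Its subject is baseline characteristics, and both tests are unadjusted in any case.

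Three stronger readings are tempting but not supported. A reader might infer that the plan has chosen the t-test as its primary analysis; it names no primary analysis. A reader might infer that poor response is certain to be properly adjusted while the primary count is not; the plan says multivariate but lists no covariates. A reader might infer that an adjusted model would isolate the effect of letrozole; neither country contributes to both stimulated cohorts, so it cannot.

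**Conclusion.** The concern holds as an omission in the analysis plan; the sample-size arithmetic is correct. A non-randomised, country-split primary comparison has no adjusted analysis, although suitable baseline covariates are collected. Under the assumed range, the unadjusted test carries a bias of 0.08 to 0.60 oocytes and a null rejection of 5.3% to 20%, with 0.24 and 7.3% mid-range and negligible harm at the low end. The documents do not show that any such imbalance exists, so it would be wrong to conclude that the primary result will be biased. Nor is the adjusted model shown to hold 5% in a multicentre study: with an assumed ICC of 0.01 to 0.05 and 3 to 6 centres per country it rejects in about 7% to 27%, against 12% to 28% for the t-test. This should be fixed before the data are analysed; the benefit is conditional on the assumed imbalance.

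**What to change.** In Section 5:

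1. Name the primary analysis: linear regression of the number of mature oocytes on cohort with robust standard errors, reporting the adjusted mean difference with 95% CI.
2. Prespecify pre-stimulation covariates already collected under Section 3.2: age at diagnosis, baseline AMH (measured centrally, Section 4.3), BMI, prior infertility treatment, and prior gynaecological surgery or history with possible impact on fertility. Do not adjust for variables that follow the start of stimulation.
3. Keep the two-sample t-test as an unadjusted sensitivity analysis.
4. Add start type (follicular or random) in a sensitivity model. Section 4.1 ties it to cycle phase at referral, whereas Sections 3.2 and 5 record it as a feature of the stimulation protocol, so its status as a baseline factor is open.
5. State that adjustment removes only measured case mix and cannot separate letrozole from country or centre practice, so the conclusion compares the Belgian letrozole programme with the French standard programme.
6. State that the 0.80 power and the model's nominal 5% error assume no between-centre variation, and report a centre-clustered sensitivity analysis.

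The cost is wording and a little more analysis work, with no new data. Precision changes slightly (simulated half-width 0.94 to 1.06, against 1.05). The clustered interval will be wider: with a small-sample-corrected method, 3 to 6 centres per country and ICC 0 to 0.05 (all assumed), the simulated median half-width was 1.08 to 2.34 oocytes.

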### **3. METHODOLOGY**

This is a multicenter hospital-based prospective cohort study conducted in institutions with known expertise in performing controlled ovarian stimulation for embryo/oocyte cryopreservation. The study aims at refining the understanding of the efficacy and safety of controlled ovarian stimulation with or without letrozole in young women with newly diagnosed breast cancer who are candidates to receive (neo)adjuvant chemotherapy.

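### The stated power of 0.80 assumes no between-centre variance, although each centre feeds only one stimulated cohort; any such variance enters the primary contrast in full, and section 5 makes no allowance for it

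*Combined protocol and SAP*

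**What the plan says.** The sample-size paragraph of section 5 (STATISTICS) takes 113 women in each stimulated cohort and claims that "the study will have a power of 0.80 to reject the null hypothesis of equal means". The assumed means are 6.1 (standard) and 7.6 (letrozole), a difference of 1.5, with a common SD of 4.0 and alpha 0.05. The test behind the figure is named at the end of that sentence: "using a two-sided two-sample equal-variance t-test". The synopsis gives the same calculation.

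The cohort definitions in section 5 and the synopsis separate the stimulated women by country. Letrozole-stimulated women "undergo oocyte/embryo cryopreservation at the Belgian participating centres"; standard-stimulated women "undergo oocyte/embryo cryopreservation at the French participating centres". Section 1 explains why: letrozole is not permitted for ovarian stimulation in France. All efficacy comparisons are letrozole against standard. The non-stimulated cohort recruits at every centre but takes no part in those comparisons.

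Section 3 (METHODOLOGY) states: "This is a multicenter hospital-based prospective cohort study conducted in institutions with known expertise". The text available does not say how many institutions there are.

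For outcome analysis, section 5 names logistic models for dichotomous outcomes, and Kaplan-Meier, log-rank and Cox methods for times to event. It names no analysis for the number of mature oocytes apart from the t-test in the sample-size statement. It contains no ICC, design effect, centre term or clustered variance.

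**The concern.** A two-sample t-test treats the 226 women as 226 independent observations. Women treated in the same clinic may resemble each other in yield. If each clinic supplied women to both cohorts, clinic differences could be removed by comparing within clinic. Here no clinic does so, and the primary contrast is made wholly between clinics, as in a cluster-allocated study. Any between-centre variance therefore adds to the variance of the cohort difference, and the t-test's standard error leaves it out.

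Two consequences follow if the ICC is above zero. Differences among a few clinics can reach p < 0.05 more often than 5% of the time with no letrozole effect. And an analysis that corrects for this has less power than 0.80.

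Adjusting for patient covariates would not in general repair the standard error, so the point is distinct from confounding by country.

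**Working it through.** **Inputs from section 5.** n = 113 per cohort, difference 1.5, SD 4.0, two-sided alpha 0.05.

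**Inputs assumed, because the documents do not give them.** k = 3, 5 or 8 equal-sized centres per country; ICC 0.01 or 0.05; total SD held at 4.0. The between-centre SD is 4 × √ICC, so these ICCs mean centre averages varying with an SD of 0.4 oocytes (ICC 0.01) or 0.9 oocytes (ICC 0.05).

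**Step 1: reproduce the stated power.** The standard error under independence is 4 × √(2/113) = 0.532, and 1.5/0.532 = 2.819. Power is 0.801 by exact noncentral t on 224 degrees of freedom and 0.805 by normal approximation. The required n by exact t is 112.6, rounded up to 113. The plan's figure is correct under independence.

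**Step 2: design effect.** DE = 1 + (m − 1) × ICC, with m = 113/k women per centre. The true standard error is 0.532 × √DE. Example with k = 5 and ICC 0.05: m = 22.6, DE = 1 + 21.6 × 0.05 = 2.08, and 113/2.08 gives about 54 effective women per cohort.

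**Step 3: behaviour of the unadjusted t-test** (normal approximation).
- Type I error = 2 × [1 − Φ(1.96/√DE)]
- Rejection rate at a true difference of 1.5 ≈ Φ((2.819 − 1.96)/√DE), plus a small opposite-tail term

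**Step 4: power of a test that holds 5%.**
- Normal approximation: Φ(2.819/√DE − 1.96)
- Centre-level degrees of freedom: noncentral t on 2k − 2 degrees of freedom with noncentrality 2.819/√DE

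| Centres per country | ICC | DE | Unadjusted: type I error | Unadjusted: rejection rate at 1.5 | 5% test: power, normal | 5% test: power, t on 2k − 2 df |
|---|---|---|---|---|---|---|
| 3 | 0.01 | 1.37 | 0.094 | 0.769 | 0.674 | 0.452 |
| 5 | 0.01 | 1.22 | 0.076 | 0.782 | 0.724 | 0.612 |
| 8 | 0.01 | 1.13 | 0.065 | 0.790 | 0.755 | 0.693 |
| 3 | 0.05 | 2.83 | 0.244 | 0.697 | 0.388 | 0.253 |
| 5 | 0.05 | 2.08 | 0.174 | 0.725 | 0.498 | 0.406 |
| 8 | 0.05 | 1.66 | 0.128 | 0.748 | 0.591 | 0.532 |

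**Step 5: check by simulation** (20,000 runs per setting). With 5 centres the unadjusted test rejected a true null in 0.075 of runs at ICC 0.01 and 0.180 at ICC 0.05. At a true difference of 1.5 it rejected in 0.785 and 0.724. With 3 centres the null rejection rates were 0.089 and 0.249.

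**Step 6: boundary cases.**
- At ICC 0 the unadjusted test keeps 0.05 and 0.80. A test on centre-level degrees of freedom would still have power of only 0.57, 0.70 and 0.75 at 3, 5 and 8 centres, so part of the loss in the last column is the price of the correction.
- With 15 centres per country and ICC 0.01, DE = 1 + 6.53 × 0.01 = 1.065. Type I error is 0.058, and a test that holds 5% has power 0.78, or 0.75 with centre-level degrees of freedom.

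**The case against.** The strongest reply is that the size is unknown. Nothing in the documents fixes the ICC or the number of centres, and with many centres and a small ICC the effect is minor. This stands. Title and contact pages and the appendix figure are absent from the text reviewed, so the missing centre list is not itself a fault of the plan.

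A reader might infer that the planned t-test's own power collapses to 0.50 or below. It does not: the 0.80 belongs to the unadjusted test, whose rejection rate falls only to 0.77–0.79 at ICC 0.01 and 0.70–0.75 at ICC 0.05. The low powers belong to a corrected test, and no single analysis has both the inflated error and the low power.

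A reader might also infer that the protocol shows practice varying by site. The support is partial. Section 4.1 allows a dose range and several ways to start, but ties the choice of start to cycle phase at referral, which is a patient factor, and does not say who sets the dose. Section 4.2 concerns vitrification and warming, which follow collection and cannot affect the number of oocytes collected. Section 3 limits participation to experienced institutions. None of this establishes an ICC of zero, but none of it demonstrates a large one.

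Finally, the t-test is named only for the sample size, so calling it the planned primary analysis is an inference. If it is not the plan, the primary endpoint has no stated analysis, and one has to be written in either case.

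**Conclusion.** The point holds in conditional form. That each centre belongs to one stimulated cohort, and that section 5 does not allow for it, are plain from the documents. For any ICC above zero, the t-test's standard error is too small and its type I error exceeds 0.05.

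The size depends on the assumed ICC and number of centres. For 3 to 8 equal-sized centres per country, type I error runs from about 0.09 down to 0.065 at ICC 0.01 and from 0.24 down to 0.13 at ICC 0.05. With about 15 centres and ICC 0.01 the problem is small. The main fault of the unadjusted test is false positives; most of the power loss appears once the test is made valid.

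The documents do not support an unconditional statement that the study is underpowered or its error rate inflated by a known amount. Nor would a centre term make the contrast causal: letrozole remains wholly confounded with country.

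**What to change.** 1. In section 5, name the primary analysis of mature oocytes. Use a model with a centre random effect, or centre-clustered standard errors, in either case with a small-sample degrees-of-freedom correction.
2. Use the same allowance for centre in the secondary efficacy comparisons of the two stimulated cohorts.
3. State the number of centres per country. Present 0.80 as conditional on ICC = 0, next to a power range over plausible ICCs (for example 0.01 to 0.05) calculated for the actual centres and for the test chosen, including its degrees of freedom.
4. State that this does not address confounding with country, which needs its own treatment.

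The cost is SAP text, wider confidence intervals and, when centres are few, a clearly lower stated power: for example 0.61 at 5 centres per country and ICC 0.01 with centre-level degrees of freedom. No extra patients are needed for the change, and it does not restore the power to 0.80.
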